4.1.3. Duration of Shedding Objective

Objective: To separately estimate and test the efficacy of HCQ and HCQ + azithromycin placebo to reduce SARS-CoV-2 viral shedding in high and low risk participants combined.

Outcome: Time to clearance of nasal SARS-CoV-2, defined as 2 consecutive negative swabs (swabs collected daily Day 1 through Day 14).

Cohort: mITT Viral Shedding Cohort

Data sets: HCQ VS Data Set, HCQ+A VS Data Set

Endpoint: The endpoint time will be set as the day of the first negative swab. Hospitalization and death are also competing risks for this outcome; however, clearance is a positive outcome whereas hospitalization and death are negative outcomes that may impede our ability to detect clearance. Participants who are hospitalized or die will have their event time censored at day 14. Other participants who do not have 2 consecutive negative tests will be censored on the day of their last positive test.

Analysis details:

Same as Section 4.1.1.

5. INTERIM MONITORING

A Data Monitoring Committee (DMC) will be convened to monitor the progress of the study. This will include study outcomes as well as futility and efficacy on the LRTI endpoint.

On July 23, 2020, the DSMB met and enrollment into the trial was stopped on July 28, 2020 for operational futility. No interim analyses were performed.

6. SAFETY ANALYSES

All safety analyses will be performed on the ITT cohort with outcomes presented by randomization arm reported overall and stratified by high and low risk.

6.1. QT PROLONGATION

To investigate whether the interventions lead to QT prolongation as measured by Corrected QT interval (QTc), we will create boxplots of QTc by study day and arm. To test for an overall difference between arms, we will fit linear mixed effects models of QTc post randomization through day 14 with random intercepts and time slopes. Randomization arm will be a main effect with additional main effect adjustments for time, age, sex, site and cohort.

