
COVID-19: coronavirus disease; EOS: end of study; Flu-PRO: inFLUenza patient-reported outcome; HCQ: hydroxychloroquine; HIPAA: Health Insurance Portability and Accountability Act of 1996; SARS-CoV-2: severe acute respiratory syndrome coronavirus 2; SpO2: oxygen saturation; WHO: World Health Organization.
 
Note: ## 800 mg-200 mg LPV/r twice a day or placebo (ascorbic acid 1 gm) twice a day.
 
Note: # denotes 400 mg-100 mg LPV/r twice a day +placebo (ascorbic acid 500 mg) twice a day
 
^a Screening and Day 1, 2, 4, 9, and 14 evaluations will be conducted through a web-based screening tool, HIPAA-compliant video conference (Telehealth), telephone, or text messaging. Screening (Day 0) and Day 1 evaluations may occur on the same day.
 
^b For patients who are hospitalized on Day 28, the last visit will be ±3 days after discharge. The exit survey may also be conducted before day 28 if a participant terminates early and is willing.
 
^c Last day of study medication will be administered on Day 10 LPV/r, and ascorbic acid.
 
^d Last day of QT monitoring will be Day 11.
 
^e These evaluations will be as needed/requested by study participant.
 
*May be omitted if not standard of care to monitor QTc for regimen
											

3. Introduction

This is a randomized, multi-center, placebo-equivalent (ascorbic acid + folic acid)-controlled, blinded platform trial for the treatment of severe acute respiratory syndrome coronavirus 2 (SARS-CoV-2) infection in high-risk adults not requiring hospital admission. The trial will start with hydroxychloroquine (HCQ) (Intervention A), HCQ + azithromycin (Intervention B), and lopinavir-ritonavir (LPV/r) (Intervention C) as experimental interventions. Additional arms will be added as new agents or combinations are prioritized. In addition, if other agents are found to be effective, HCQ, HCQ + azithromycin, or LPV/r may become the control group against which new interventions are measured. Evaluations include safety and tolerability, SARS-CoV-2 viral shedding, and development of lower respiratory tract infection (LRTI). There will be 4 study arms (Arm 1: HCQ + placebo [folic acid], Arm 2: HCQ + azithromycin, Arm 3: LPV/r and Arm 4: placebo [ascorbic acid +/- folic acid],) enrolled to assess a daily dosing regimen administered for 10 days to prevent LRTI or decrease the time to symptom resolution and decrease viral shedding.

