The most common adverse reactions to azithromycin are diarrhea, nausea, abdominal pain, or vomiting (Zithromax USPI, Appendix 6). Severe side effects include serious allergic reactions, including, but not limited to, anaphylaxis, angioedema, and dermatologic reactions such as Stevens-Johnson syndrome. Abnormal liver function, hepatitis, cholestatic jaundice, hepatic necrosis, and hepatic failure have been reported, some of which have resulted in death. Azithromycin can cause abnormal changes in the cardiac electrophysiology that may lead to a potentially fatal irregular heart rhythm. It may increase the risk of death, especially in those with heart problems, compared with those on other antibiotics such as amoxicillin or no antibiotic. The FDA warning indicated that people with pre-existing conditions are at particular risk, such as those with QT interval prolongation, proarrhythmic conditions, low blood levels of potassium or magnesium, a slower than normal heart rate, or those who use certain drugs to treat abnormal heart rhythms. Elderly patients may be more susceptible to development of torsades de pointes arrhythmias.

7.2.3. *QT Risks Associated with Coadministration of HCQ and Azithromycin*

Combination treatment with HCQ + azithromycin was associated with heart-rate corrected QT interval (QTc) prolongation in a study of 84 patients with SARS-CoV-2 (Chorin 2020). Maximal QTc prolongation was observed between Days 3 and 4 of treatment. QTc increase from baseline

was >40 ms in 30% of the patients and 11% exhibited severely prolonged QTc, defined as a maximum increase to >500 ms. Multivariate analysis showed that the development of acute renal failure rather than baseline QTc was a significant predictor of severe QTc prolongation in these patients.

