2.1. BASELINE DATA

The following baseline variables will be described: age, sex, presence of known COVID-19 risk factors (includes all factors that categorize participants into the high-risk category), race/ethnicity and time since onset of symptoms.

Baseline variables will be summarized overall and within high and low risk strata by treatment arm. Because of the potential for imbalance between arms due to household-based randomization, statistical testing across arms will be performed using gee adjusted by risk strata with exchangeable correlation within household. If there appears to be imbalance across the arms, ($p<0.10$), the variable will be adjusted for in primary analyses.

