7.4. MAGNITUDE OF VIRAL SHEDDING

Objective: To test whether HCQ or HCQ + azithromycin is associated with decreased viral shedding from self-collected nasal swabs over 14 days compared to placebo

Outcomes: Quantity of SARS-CoV-2 detected from mid-nasal swabs by PCR as measured by cycle threshold (Ct)

Cohort: mITT Cohort

Data sets: VS Data Set

Analysis details: Generalized linear mixed effects models with random intercepts and slopes (time) will be used to model the quantity of SARS-CoV-2 over time. Because of the high number of samples where Ct was above the upper limit (eg >40) and not recorded, we will do analyses with Ct dichotomized as follows:

- Ct>40 on both targets vs Ct<=40 on either target
- Concordant results vs discordant or negative
- Ct<24 on either target as this may be an indicator of greater propensity to be infectious[2].

Fixed effects will include randomization arm, B-spline coefficients for time, an interaction between arm and time, cohort, age, and other baseline covariates indicated for the primary analysis. Time will be the time since enrollment visit to collection of the sample.

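### The QTc model in SAP 6.1 allows only one constant arm effect, so it can understate an early, transient prolongation on HCQ + azithromycin

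*SAP*

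**What the plan says.** SAP 6.1 gives QTc two analyses. The first is descriptive: "we will create boxplots of QTc by study day and arm". The second is a test, whose aim is introduced as "To test for an overall difference between arms"; for it, "we will fit linear mixed effects models of QTc post randomization through day 14 with random intercepts and time slopes". The fixed effects are then listed: "Randomization arm will be a main effect with additional main effect adjustments for time, age, sex, site and cohort". The list has no interaction between arm and time and no baseline QTc. SAP 2.1 does not list QTc among the baseline variables either ("The following baseline variables will be described: age, sex, presence of known COVID-19 risk factors", then race/ethnicity and time since symptom onset).

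Protocol 7.2.3 describes a cited study of 84 patients on HCQ + azithromycin: "Maximal QTc prolongation was observed between Days 3 and 4 of treatment". Azithromycin is given on Days 1 to 5 and HCQ on Days 1 to 10 (Protocol 3.2.4, 3.2.7 and 7.1). Footnote d of the Schedule of Activities states: "Last day of QT monitoring will be Day 11". Protocol 9.2 likewise limits ECGs to Day 11.

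The SAP does let the arm effect vary with time for other outcomes. Section 7.2 adds a randomisation-by-time interaction for Flu-PRO. Section 7.4 uses "B-spline coefficients for time, an interaction between arm and time" for viral quantity.

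**The concern.** The random slopes in SAP 6.1 belong to individuals, not to arms. The fixed part therefore forces the arm difference to be the same on every day. If the true difference rises to a maximum on Days 3 to 4 and then declines, the single coefficient mixes peak days with weaker days. It then falls below the effect that matters most for cardiac safety.

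Two features of the plan can add to this. Protocol 8.1 lists prolonged QT as a reason to stop study product while evaluations continue, and SAP section 6 analyses safety by ITT. Strong responders may therefore contribute later off-drug readings to their randomised arm. In addition, randomisation is on Day 0 and the first ECG is on Day 1, so a pre-dose Day 1 reading would count literally as a post-randomisation outcome.

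This is the only formal QTc comparison in the SAP, and it concerns drugs that the protocol itself describes as QT-prolonging.

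**Working it through.** The documents give no QTc sample size, SD or target difference, so there is no planned figure to reproduce. The check asks what the SAP 6.1 arm coefficient would estimate under different true time courses.

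**Model.** QTc = b0 + b1·t + θ·arm + u + v·t + e, with SDs σu, σv and σe. Per person, V = Z·diag(σu², σv²)·Zᵀ + σe²·I. With equal arms and a true arm difference δ by day, the expected estimate of θ is the arm element of (X0ᵀV⁻¹X0 + X1ᵀV⁻¹X1)⁻¹X1ᵀV⁻¹δ. The other covariates do not change this expectation under randomisation.

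**From the documents.** Maximum on Days 3-4 (Protocol 7.2.3), ECGs to Day 11, azithromycin half-life 79 hours (Protocol 3.2.7), HCQ half-life about 40 days (Protocol 3.2.4).

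**Assumed.** Daily ECGs on Days 2-11; σu and σe each 15 or 20 ms; σv 0, 0.5, 1 or 2 ms/day; time counted from Day 0 or Day 1. The first five curves rise linearly from 0 on Day 1 to 1 at Day 3.5.

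Expected coefficient as a share of the maximum effect:

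| Course of the arm difference | σv = 0 | σv = 0.5 | σv = 1 | σv = 2 | True mean, Days 3-4 |
|---|---|---|---|---|---|
| Linear fall to 0 by Day 14 | 0.62 | 0.63-0.64 | 0.66-0.69 | 0.73-0.79 | 0.88 |
| Linear fall to 0 by Day 11 | 0.49 | 0.51-0.54 | 0.57-0.63 | 0.69-0.80 | 0.87 |
| Flat to Day 5, then 79-hour half-life | 0.63 | 0.64-0.65 | 0.68-0.72 | 0.76-0.83 | 0.90 |
| Halving every 2 days | 0.39 | 0.41-0.43 | 0.46-0.52 | 0.58-0.68 | 0.82 |
| Stays at its maximum | 0.92 | 0.90-0.91 | 0.85-0.88 | 0.76-0.82 | 0.90 |
| Linear rise to Day 10 | 0.60 | 0.54-0.57 | 0.42-0.50 | 0.19-0.34 | 0.28 |

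With σv = 0 the coefficient is the plain daily mean. For halving every 2 days that is (0.40 + 0.80 + 0.84 + 0.59 + 0.42 + 0.30 + 0.21 + 0.15 + 0.11 + 0.07)/10 = 0.39. In all four transient curves (first four rows) the coefficient lies below the true Day 3-4 mean: 0.39-0.83 against 0.82-0.90. If pre-dose Day 1 readings are counted as outcomes, the same four curves give 0.35-0.61.

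**Precision and power, illustration only.** Peak 10 ms, σu = 20, σv = 1, σe = 15, time from Day 1, 100 per arm, two-sided alpha 0.05.

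- Variance of one person's Day 3-4 mean: 400 + 2.5² + 225/2 = 518.75. SE of the contrast = √(2 × 518.75/100) = 3.22 ms.
- With a pre-dose baseline (variance 400 + 225 = 625, covariance 400): 518.75 − 400²/625 = 262.75. SE = √(2 × 262.75/100) = 2.29 ms.
- SE of the SAP coefficient: 2.98 ms, or 1.94 ms with baseline, which is 35% smaller. The estimate itself does not change.

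Power = Φ(effect/SE − 1.96):

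| Course | SAP test | Day 3-4 contrast | Day 3-4 contrast with baseline |
|---|---|---|---|
| Linear fall to 0 by Day 14 | 6.8 ms, 0.63 | 8.8 ms, 0.78 | 0.97 |
| Halving every 2 days | 5.0 ms, 0.39 | 8.2 ms, 0.72 | 0.95 |
| Stays at its maximum | 8.6 ms, 0.82 | 9.0 ms, 0.80 | 0.98 |

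**The case against.** The strongest defence is that the model answers its stated question, an overall difference between arms, and that the boxplots would reveal an early peak. SAP 6.2 also tabulates cardiac events and events leading to discontinuation. If the effect is sustained, the constant-effect test loses nothing: power 0.82 against 0.80 above. This stands as far as it goes. However, section 6.1 gives its purpose as finding out whether the interventions prolong QT, and nothing in it quantifies the arm difference on the days when the protocol expects the maximum.

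Three stronger readings are tempting, and the documents do not support them.

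- **That a 20 ms peak would be reported as 8-10 ms.** This takes an effect fully present on Days 2-5 or 2-6, then absent, with equal daily weights: 4/10 = 0.40 and 5/10 = 0.50. Those shares arise only when the random-slope variance is zero, yet the SAP specifies random slopes. With σv of 0.5-2 ms/day the same step curves give 0.44-0.96 and 0.54-1.09. The quoted half-lives do not suggest an abrupt end at Day 5 or 6 either.
- **That the Day 3-4 peak applies to both active arms.** Protocol 7.2.3 reports it for the combination only. No peak day is given for HCQ alone, and ten days of dosing with a half-life of about 40 days could give a sustained or rising effect. In the rising case above, a Day 3-4 contrast would capture only 0.28 of the eventual effect.
- **That leaving out baseline QTc dilutes the effect.** In a randomised comparison it costs precision only. Nor is a clean baseline assured: no ECG is scheduled on Day 0, and Protocol 9.1 lists the Day 1 survey before dosing without stating that the ECG is pre-dose.

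**Conclusion.** The point holds in a limited form. SAP 6.1 imposes one constant arm effect on QTc, while the protocol documents an early maximum for HCQ + azithromycin. The coefficient can understate a transient peak, to roughly 0.4-0.9 of its size under the smooth curves tried (0.39-0.83 if the effect declines, 0.76-0.92 if it stays at its maximum). The amount depends on a time course and on variances that the documents do not give. The direction was the same in every transient curve, but no single dilution figure is justified. For HCQ alone, the finding is only that a constant term cannot describe an effect that changes over time.

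The missing baseline QTc is a separate matter of precision. The Day 14 window is a minor inconsistency: with no ECG scheduled on Days 12-14, it adds no planned data. The Day 11 limit is taken from the supplied protocol, which was amended when the HCQ arms stopped. The change is worth making because it is cheap and the SAP already uses such terms elsewhere.

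**What to change.** 1. Add an arm-by-time term to the QTc model, with day as a categorical factor or in the B-spline form of SAP 7.4.
2. Report by-day arm differences with 95% CIs for each active arm against control. Pre-specify a Day 3-4 contrast for HCQ + azithromycin. For HCQ alone, present the full by-day profile without singling out a peak day.
3. Adjust for Day 1 QTc where a pre-dose time is confirmed, and treat it as missing baseline otherwise. State how missing baselines are handled. Do not count pre-dose readings as post-randomisation outcomes.
4. Align the Day 14 window with QT monitoring that ends on Day 11.

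No new data collection is needed. The costs are more model parameters and a baseline that will be missing for some participants. The Day 3-4 contrast also has a slightly larger SE than the overall coefficient (3.22 against 2.98 ms in the illustration). SAP section 5 records that enrolment stopped in July 2020, and the change history dates version 1.1 to January 2022. If QTc results by arm are already known, the added analysis should be labelled supplementary and reported beside the planned one.

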6.2. ADVERSE EVENTS AND DEATHS

Serious adverse events (SAEs, including hospitalization and death), reportable adverse events leading to treatment discontinuation (RAEs), and cardiac v. non-cardiac events will be summarized in frequency tables (including both the number of each SAE/RAE and the number of distinct participants ever reporting each SAE/RAE) by severity and randomization arm, for each of the low and high risk cohorts, and overall.

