With tens of millions of doses of HCQ administered for malaria and autoimmune diseases, the side effect profile of HCQ is well described and the drug is generally well tolerated. With short-term administration (as opposed to chronic/year-long use in rheumatologic disease management), the major AEs are gastrointestinal (nausea, vomiting, dyspepsia, abdominal cramps, and diarrhea) and transient skin rashes. The gastrointestinal symptoms may vary by specific generic manufacturer of HCQ (Srinivasa 2017) and are best managed by taking the drug with food or a glass of milk (Appendix 5). A transient rash, most commonly morbilliform or psoriasiform, can develop in 10% of participants, often with a sustained loading dose, and is often managed by lowering the dose. To avoid this potential side effect, this protocol is using a short loading dose, not a sustained one. Uncommonly, idiosyncratic leukopenia/thrombocytopenia can occur and the drug should not be given to those with underlying bone marrow disorders. Lastly, hypoglycemia can occur and those taking insulin or glucose-lowering drugs are at risk; blood glucose should be monitored.

The safety of HCQ for treatment of patients with COVID-19 disease is unknown. COVID-19 may be associated with cardiac effects. HCQ may prolong QT, resulting in arrhythmias. Participants will be monitored for QT prolongation and counseled about this risk.

Long-term manifestations of HCQ, including retinitis, renal and hepatic disease, and cardiomyopathy (Appendix 5), are not likely in short-term exposure.

7.2.2. *Risks Associated with Azithromycin*

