- Participants experiencing Grade 4 toxicity requiring permanent discontinuation of study product should be followed up weekly until resolution of the AE or return to baseline. These participants will remain on study, off study treatment, and have all evaluations performed per the SoA.

Specific Management of Toxicities Related to Study-provided Drugs

HCQ

Gastrointestinal disturbance

Gastrointestinal disturbance (nausea, vomiting, dyspepsia, abdominal cramps, and diarrhea) is a common known possible side effect of HCQ. Taking with food or milk may improve tolerability.

Visual disturbances

Suspected visual changes should be evaluated for possible etiologies—if an HCQ-associated visual disturbance is suspected, HCQ should be stopped.

Allergic reactions

HCQ should be discontinued permanently if a serious allergic reaction is suspected. These participants will remain on study, off study treatment, and have all evaluations performed per the standard operating procedure(s).

QT prolongation

HCQ is associated with QT prolongation. QT will be assessed during the study using a portable monitor that can transmit electrocardiograms (ECGs) to measure the QTc to a central location, which will be monitored. Participants will be counseled about this risk.

Hypoglycemia

HCQ can be associated with hypoglycemia, particularly among patients with diabetes mellitus who are also taking insulin or sulfonylureas. Participants will be counseled about this risk.

Azithromycin

Gastrointestinal disturbance

Gastrointestinal adverse reactions (nausea, vomiting, abdominal pain, and diarrhea) are common side effect of azithromycin. Most gastrointestinal side effects do not require treatment discontinuation and participants may receive treatment for symptoms (e.g., antiemetics).

Allergic reaction

Serious allergic reactions, including, but not limited to anaphylaxis, angioedema, and dermatologic reactions such as Stevens-Johnson syndrome have been reported with azithromycin treatment. Azithromycin should be discontinued immediately in the event of a hypersensitivity reaction.

QT prolongation

Azithromycin is associated with QT prolongation. QT will be assessed during the study using a portable monitor that can transmit ECGs to measure the QTc to a central location, which will be monitored. Participants will be counseled about this risk.

LPV/r

QT prolongation

LPV/r may be associated with QT prolongation. Participants will be counseled about this risk.

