10.1.2. Participant Survey

Participants will be asked to complete surveys (Daily Surveys and Exit Contact Survey) that will include questions about symptoms from both the drug regimen and respiratory and systemic

symptom, review of concomitant medications, and other pertinent topics. A modified self-reported Flu-Pro instrument will be completed each day through Day 14 and on Day 21 and Day 28 to assess degree of illness (Yu 2020) (Appendix 12).

10.2. *Adverse Events*

Participants will be asked to complete surveys (Daily Surveys and Exit Contact Survey) that include information on any symptoms that they are experiencing. In addition, AE review by a staff member (via telephone, Telehealth, or text messaging) will be performed.

All AEs must be recorded on the electronic case report forms (eCRFs) if any of the following criteria have been met:

- All AEs meeting SAE definition
- All AEs leading to discontinuation of study medication
- All AEs judged by the site Investigator to be associated with study medication

10.2.1. *Adverse Events*

An AE is any untoward medical occurrence that occurs in a patient or clinical investigation subject administered a pharmaceutical product, which does not necessarily have to have a causal relationship with this treatment. An AE can therefore be any unfavorable and unintended sign (including abnormal laboratory findings), symptom, or disease temporally associated with the use of an investigational product, whether or not considered related to the product.

AEs may include the onset of new illness and the exacerbation of pre-existing medical conditions. An AE can include an undesirable medical condition occurring at any time, including baseline or washout periods, even if no study treatment has been administered.

10.2.2. *Serious Adverse Events*

An SAE is defined as any untoward medical occurrence that:

- Results in death
- Is life-threatening
- Requires inpatient hospitalization or prolongation of existing hospitalization
- Results in persistent or significant disability/incapacity
- Is an important medical event that may not be immediately life-threatening or result in death or hospitalization but may jeopardize the participant or may require intervention to prevent one of the other outcomes listed in the definition above

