All AEs that are recorded must have their severity graded. To grade AEs, sites should refer to the DAIDS AE Grading Table, corrected Version 2.1, July 2017, which can be found on the DAIDS Regulatory Support Center website at [https://rsc.tech-res.com/docs/default-source/safety/division-of-aids-\(daids\)-table-for-grading-the-severity-of-adult-and-pediatric-adverse-events-corrected-v-2-1.pdf](https://rsc.tech-res.com/docs/default-source/safety/division-of-aids-(daids)-table-for-grading-the-severity-of-adult-and-pediatric-adverse-events-corrected-v-2-1.pdf).

10.2.3. *Treatment-related AE and SAE*

A treatment-related adverse event is defined as any new AE that begins, or any preexisting condition that worsens in severity, after at least 1 dose of study treatment has been administered until the end of study (i.e., Day 28) and is considered by the Investigator to be related to the study medication.

All AEs and SAEs should have attribution recorded as treatment- or not treatment-related, in the judgment of the site Investigator.

10.3. *Treatment of Overdose*

Overdose of HCQ, azithromycin, or LPV/r should be managed according to the labeling information (see [Appendix 5](#), [Appendix 6](#), and [Appendix 7](#), respectively). Study drug overdose, including misuse or abuse of the product and medication errors, should be reported in the eCRF in the clinician notes.

Ascorbic acid and folic acid exhibit low toxicity; risks from overdose are expected to be minimal.

10.4. *Pregnancy*

Pregnancies occurring in participants enrolled in this study must be reported and followed to outcome. Pregnancy alone is not regarded as an AE unless there is a possibility that the study drug may have interfered with the effectiveness of a contraceptive medication. Elective abortions without complications should not be considered AEs unless they were therapeutic abortions. Hospitalization for normal delivery of a healthy newborn should not be considered an SAE. Pregnancy is not considered an SAE unless there is an associated serious outcome. Spontaneous abortions should always be reported as SAEs.

10.5. *Safety Assessments*

Safety will be assessed via participant Surveys, as shown in the SoA.

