11.3.2.1. Safety Analyses

All safety analyses will be performed on the Intention-to-Treat population. AEs will be compared by study group.

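### SAP 6.2 names by-arm tables for SAEs and for AEs that stopped treatment, but none for related, non-serious AEs in participants who stayed on treatment, although the protocol records these events and says AEs will be compared by group.

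*SAP*

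**What the plan says.** Protocol 10.2 (Adverse Events) requires an AE to go on the eCRF if it meets any one of three criteria:

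- "All AEs meeting SAE definition"
- the event caused the participant to stop the study drug
- "All AEs judged by the site Investigator to be associated with study medication"

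Recorded AEs are graded for severity (10.2.2). Under 10.2.3, "All AEs and SAEs should have attribution recorded as treatment- or not treatment-related". Protocol 11.3.2.1 (Safety Analyses) states: "AEs will be compared by study group".

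SAP 6.2 lists SAEs and then says "reportable adverse events leading to treatment discontinuation (RAEs), and cardiac v. non-cardiac events will be summarized in frequency tables", by severity and arm, for each risk cohort and overall. Its parenthesis on what is counted refers to SAEs and RAEs. The safety endpoint in SAP Table 1 has the same two parts: SAEs, and AEs that resulted in stopping treatment.

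On expected harm, Protocol 7.2.1 says of short-term HCQ that "the major AEs are gastrointestinal (nausea, vomiting, dyspepsia, abdominal cramps, and diarrhea) and transient skin rashes". Protocol 7.4 says of azithromycin: "Most gastrointestinal side effects do not require treatment discontinuation". The same section lets participants with related Grade 1 or 2 toxicity stay on treatment at the site investigator's discretion.

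**The concern.** The protocol asks sites to record, grade and attribute related AEs whether or not they are serious and whether or not treatment stopped. The SAP is the document that turns this into tables, and its table rule selects on seriousness and discontinuation. A drug effect that is unpleasant but tolerated passes neither test.

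If the section is followed as written, the AE tables could look similar between arms even if an active arm carried more nausea, diarrhea or rash. For outpatients with mild illness, tolerability is a large part of the benefit-risk judgement. The information would be missing from the report because of how the table is defined, not because it was never collected.

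**Working it through.** No plan figure needs to be reproduced. The check sets what is recorded against what is tabulated.

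**Step 1: recorded classes against named tables.**

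| Class on the eCRF (Protocol 10.2) | Named in SAP 6.2 |
|---|---|
| SAE | Yes |
| AE leading to discontinuation | Yes, as RAE |
| Related AE, non-serious, treatment continued | No explicit table |

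Three classes are recorded and two have a named table. The cardiac versus non-cardiac item is undefined. If it splits all recorded events, it would reach the third class. If it splits SAEs and RAEs, it would not. The parenthesis, which counts only SAEs and RAEs, favours the second reading without settling it.

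**Step 2: is the third class reported elsewhere in the SAP?**

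- SAP 6.1 analyses QTc by day and arm whether or not treatment stopped. It covers that harm only.
- SAP 7.2 reports the modified Flu-PRO by arm, as a mean over all symptoms.
- SAP 8 covers temperature, oxygen saturation, heart rate and respiratory rate.

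None of these tabulates related AEs.

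**Step 3: can the Flu-PRO mean stand in?** Protocol Appendix 12 lists 5 nose, 4 throat, 3 eye, 7 chest, 4 gastrointestinal and 11 body items: 5 + 4 + 3 + 7 + 4 + 11 = 34. The four gastrointestinal items are nausea, stomach ache, vomiting and diarrhea. No item covers rash. If response categories are scored in unit steps (an assumption), a one-category worsening on all four gastrointestinal items moves the mean by 4/34 = 0.12. SAP 7.2 also analyses the score as disease severity, so drug toxicity and symptom benefit would offset each other within it.

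**Step 4: which events fall in the third class?** Protocol 7.4 treats the grades differently.

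- Related Grade 1 or 2: treatment may continue. Some participants will stop, and their events become RAEs. The rest do not.
- Related Grade 3, symptomatic: product is withheld and may be reintroduced. Permanent discontinuation is described separately. SAP 6.2 does not say whether a temporary hold makes an event an RAE. If it does not, a related, non-serious Grade 3 event could also go untabulated.
- Grade 4, symptomatic: product is permanently discontinued, so the event would be an RAE.

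**Step 5: size.** The number omitted per arm would be the participants with a related AE minus those whose related AE was serious or stopped treatment. The documents give neither term for these regimens, so it cannot be estimated.

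**The case against.** The strongest reply is that SAP 6.2 implements the declared safety endpoint. SAP Table 1 defines safety for these arms as SAEs and AEs that stopped treatment, and 6.2 tabulates those. That is correct, and 6.2 is not at odds with the endpoint. But Protocol 10.2 and 11.3.2.1 go further than the endpoint, and a statement that AEs will be compared by group needs a table to carry it out.

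Four stronger readings are tempting and should not be drawn.

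- A reader might infer that related AEs will never be reported by arm. Protocol 11.3.2.1 commits to comparing AEs, nothing in the SAP withdraws that, and the cardiac item is open to a wider reading. What can be said is that the SAP names no such table.
- A reader might apply the 10% rash figure in Protocol 7.2.1 to the 165 per arm in SAP 1.5.1 (0.10 x 165 = 16.5). The protocol links that figure often to a sustained loading dose and says its short loading dose is meant to avoid the effect. The 165 is an initial target, and SAP 5 records that enrollment stopped early. The product is not an expected count for this trial.
- A reader might argue that attribution is unreliable because the tablets differ visibly. Protocol 7.6.1 says HCQ and ascorbic acid appear similar and that study clinicians do not see the medication. Azithromycin and folic acid differ in shape, and LPV/r differs from ascorbic acid, but relatedness is the site investigator's judgement.
- A reader might conclude that the main expected harm is ignored. QT prolongation is also a stressed risk, and SAP 6.1 analyses it regardless of discontinuation.

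**Conclusion.** The point holds as a mismatch between the protocol's safety commitment and the SAP's table specification. One of three recorded AE classes, related AEs that were non-serious and did not stop treatment, has no explicit by-arm table. On the protocol's own account this class contains much of the expected gastrointestinal toxicity, and any rash in participants who continued. It may also contain Grade 3 events managed by a temporary hold. The Flu-PRO mean does not fill the gap.

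The size in events is unknown, and the conclusion does not depend on it. It rests on two readings: that the cardiac split applies to SAEs and RAEs, as the parenthesis suggests, and that RAE means what its wording says. If the authors meant otherwise, the section still needs to say so.

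The SAP covers the three arms first implemented. For LPV/r, the protocol's endpoint has the same two parts, but 11.3.2.1 applies to that comparison too and no SAP for it is among the documents. A reader might infer that the LPV/r endpoint must be amended. It need not be, because an endpoint does not have to list every safety table.

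**What to change.** In SAP 6.2:

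1. Add a by-arm table of all AEs recorded on the eCRF, including related AEs, by grade and organ system, overall and by risk cohort. Give between-arm differences with 95% confidence intervals for gastrointestinal AEs and for rash.
2. State whether the cardiac versus non-cardiac summary covers all recorded AEs or only SAEs and RAEs.
3. State whether RAE includes temporary withholding of study product or only permanent discontinuation. This is a reporting definition and changes no treatment rule.
4. As a supplement that does not depend on attribution, tabulate by arm the four gastrointestinal Flu-PRO items collected daily. Under Protocol 10.2, a non-serious event that did not stop treatment must go on the eCRF only if judged related, so the AE table alone cannot show those judged unrelated.

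Carry the same table into the LPV/r SAP so that Protocol 11.3.2.1 is met there.

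The cost is SAP wording and a few tables from data already specified for collection. The downside is a longer safety section, and any table added after unblinding must be labelled as such.
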